## 5.5 Treatments

#### 5.5.1 Identity of investigational product

The investigational product used in this study is presented in Table 2.

Table 2	Identity of investigational product
---------	-------------------------------------

Investigational product	Dosage form and strength	Manufacturer
Ticagrelor	90 mg tablets	AstraZeneca

The investigational product is supplied to by AstraZeneca, Sweden as study qualified person (QP) released specific labelled bulk. The personnel will prepare the investigational product for each healthy volunteer according to the Handling Instructions provided by AstraZeneca and the randomisation scheme. will be the final QP releasing site.

#### 5.5.2 Doses and treatment regimens

#### Investigational product, dosage and mode of administration

Each healthy volunteer will receive a single dose of ticagrelor in three different ways.

- A. Ticagrelor 90 mg as a whole tablet. The ticagrelor tablet should be swallowed whole with 200 mL room temperature water and should not be split, chewed or crushed.
- B. Crushed ticagrelor 90 mg tablet suspended in water according to handling instructions, administered as a single oral dose with 200 mL water, including 75 mL used to rinse the container (3 rinses of 25 mL each) used for dose preparation.
- C. A crushed ticagrelor 90mg tablet, suspended in water and administered through a nasogastric tube into the stomach. The total volume of water used for investigational product administration will be 200 mL including 75 mL of water to rinse the container (3 rinses of 25 mL each) used for preparation of dose and 25 mL of water used to flush the nasogastric tube.

For administration via nasogastric tube, the tablet should be crushed and mixed with water. The suspension should be drawn into a syringe and infused into the nasogastric tube.

The time point of the last drop of water consumed (orally) or injected through the nasogastric tube for investigational product administration will be considered as the timing for administration of the investigational product.

#### 5.5.3 Labelling

The bulk bottles will be labelled by AstraZeneca Research and Development (R&D) Mölndal, Sweden according to Good Manufacturing Practice (GMP). Labels will fulfil GMP Annex 13 requirements for labelling and all local regulatory requirements. The dose containers will be supplied and labelled by . The dose container labels will be supplied by AstraZeneca. The containers will be labelled with a 2 panel label. One part of the label will be permanently affixed to the container and the other part will be peel-off part for insertion in the healthy volunteer's electronic Case Report Form (eCRF).

#### 5.5.4 Storage

All study drugs must be kept in a secure place under appropriate storage conditions. The investigational product label on the containers specifies the appropriate storage.

The dispensing and retention of reserve samples of the investigational product will be performed with the FDA Code of Federal Regulations 21, Part 320 Bioavailability and Bioequivalence requirements (Guidance for Industry 2003).

## 5.6 **Concomitant and post-study treatment(s)**

No concomitant medication or therapy will be allowed except for systemic contraceptives as described in Appendix E and occasional use of paracetamol/acetaminophen is allowed for minor pains and headache during the study. No other prescription or over-the-counter drugs are allowed as specified in the exclusion criteria and restrictions. The volunteers must be instructed that no additional medication will be allowed without the prior consent of the Investigator.

Other medication, which is considered necessary for the volunteer's safety and well being, may be given at the discretion of the Investigator and recorded in the appropriate sections of the eCRF.

## 5.7 Treatment compliance

The administration of the investigational product should be recorded in the appropriate sections of the eCRF.

## 5.7.1 Accountability

The investigational product provided for this study will be used only as directed in the CSP. The study personnel will account for all study drugs dispensed to and returned from the healthy volunteer.

Study site personnel will account for all study drugs received at the study centre, unused study drugs and for appropriate destruction. Destruction must not take place unless the responsible at AstraZeneca has approved it. Certificates of delivery and destruction must be signed.

## 5.8 Discontinuation of investigational product

Volunteers may be discontinued from investigational product and assessments in the following situations:

• Volunteer decision. The volunteer is at any time free to discontinue treatment, without prejudice to further treatment

- Adverse Events (including inter-current illness), laboratory variable, vital signs measurement, or ECG changes are seen during or after administration of the investigational product which would indicate that any further administration may have an impact on the safety of the volunteer, administration must be stopped or further study treatment must be discontinued, in particular for laboratory values of special interest
- Risk to volunteers as judged by the Investigator and/or AstraZeneca
- Severe non-compliance to study protocol as judged by the Investigator and/or AstraZeneca
- Volunteers who do not meet the selection criteria are randomised in error or incorrectly started on treatment, or where volunteers subsequently fail to meet the study criteria post-initiation (a discussion should occur between the AstraZeneca CPA Physician and the Investigator regarding whether to continue or discontinue the volunteer from the investigational product).

#### 5.8.1 **Procedures for discontinuation of a subject from investigational product**

A volunteer that decides to discontinue the investigational product will always be asked about the reason(s) and the presence of any AEs. If possible, they will be seen and assessed by the Investigator. Adverse events will be followed up (See Sections 6.3.3 and 6.3.4).

If a volunteer is withdrawn from study, see Section 5.9.

## 5.9 Withdrawal from study

Volunteers are at any time free to withdraw from study (investigational product and assessments), without prejudice to further treatment (withdrawal of consent). Such volunteers will always be asked about the reason(s) and the presence of any AEs. If possible, they will be seen and assessed by the Investigator. Adverse events will be followed up (See Sections 6.3.3 and 6.3.4).

At the discretion of AstraZeneca, volunteers that withdraw from the study may be replaced.

## 6. COLLECTION OF STUDY VARIABLES

Refer to Table 1 for the study assessments. When more than 1 assessment is required at a particular time point, PK samples should be prioritised.

## 6.1 Recording of data

The Investigator will ensure that data are recorded on the eCRFs as specified in the study protocol and in accordance with the instructions provided.

The Investigator ensures the accuracy, completeness, and timeliness of the data recorded and of the provision of answers to data queries according to the Clinical Study Agreement. The Investigator will sign the completed eCRFs. A copy of the completed eCRFs will be archived at the study centre.

## 6.2 Data collection at enrolment and follow-up

#### 6.2.1 Enrolment procedures

Each volunteer will undergo screening to confirm eligibility. This will consist of the following:

- Obtaining written informed consent before starting any study-specific procedures
- Review of the inclusion/exclusion criteria with the volunteer
- Recording of demographic data (date of birth, age and gender)
- A standard recording of relevant medical and surgical history
- A complete physical examination
- Height, weight, and calculation of BMI
- 12-Lead paper ECG
- Vital signs (BP and pulse rate)
- Blood sampling for routine clinical chemistry and haematology measurements, for FSH assessment (in self declared post-menopausal female volunteers) and a HBsAg, antibodies to HCV, and HIV screen
- Urine sampling for routine urinalysis
- Urine pregnancy test in female volunteers only
- Urine sampling for drugs of abuse and alcohol screening
- Adverse events and serious adverse events (SAEs) will be recorded (if any)
- Prior and concomitant medication recording (done on Day -1)
- After admission and before randomisation the investigator should reassess each volunteer to reconfirm eligibility.

#### 6.2.2 Follow-up procedures

Volunteers will return to the study centre for follow-up 5 to 10 days after the last dose of the investigational product. The follow-up visit will include the following:

- A complete physical examination
- 12-Lead paper ECG
- Vital signs (BP and pulse rate)
- Blood sampling for routine clinical chemistry and haematology measurements
- Urine sampling for routine urinalysis
- Urine pregnancy test in female volunteers only
- Concomitant medication recording
- Adverse events and SAEs will be recorded.

## 6.3 Safety

The Investigator is responsible for ensuring that all staff involved in the study is familiar with the content of this section.

#### 6.3.1 Definition of adverse events

An AE is the development of an undesirable medical condition or the deterioration of a pre-existing medical condition following or during exposure to a pharmaceutical product, whether or not considered causally related to the product. An undesirable medical condition can be symptoms (eg, nausea, chest pain), signs (eg, tachycardia, enlarged liver) or the abnormal results of an investigation (eg, laboratory findings, ECG). In clinical studies, an AE can include an undesirable medical condition occurring at any time, including run-in or washout periods, even if no investigational product has been administered.

The term AE is used to include both serious and non-serious AEs.

#### 6.3.2 Definitions of serious adverse event

An SAE is an AE occurring during any study phase (ie, run-in, treatment, washout, follow-up), that fulfils one or more of the following criteria:

- Results in death
- Is immediately life-threatening
- Requires in-patient hospitalisation or prolongation of existing hospitalisation

- Results in persistent or significant disability/incapacity or substantial disruption of the ability to conduct normal life functions
- Is a congenital abnormality or birth defect
- Is an important medical event that may jeopardise the volunteer or may require medical intervention to prevent one of the outcomes listed above.

For further guidance on the definition of an SAE, see Appendix B to the CSP.

#### 6.3.3 Recording of adverse events

#### Time period for collection of adverse events

Adverse events will be collected from the time of signature of informed consent throughout the treatment period and including the follow-up period.

All SAEs will be recorded from the time of informed consent.

#### Follow-up of unresolved adverse events

Any AEs that are unresolved at the volunteer's last visit in the study are followed up by the Investigator for as long as medically indicated, but without further recording in the eCRF. AstraZeneca retains the right to request additional information for any volunteer with ongoing AE(s)/SAE(s) at the end of the study, if judged necessary.

#### Variables

The following variables will be collected for each AE;

- Adverse event (verbatim)
- The date and time when the AE started and stopped
- Intensity, rated according to the following scale:
  - Mild (awareness of sign or symptom, but easily tolerated)
  - Moderate (disturbing but still tolerable)
  - Severe (incapacitating, with inability to perform normal activities).
- Whether the AE is serious or not
- Investigator causality rating against the investigational product (yes or no)
- Action taken with regard to the investigational product
- Adverse event caused the volunteer's withdrawal from study (yes or no)

• Outcome.

In addition, the following variables will be collected for SAEs:

- Date AE met criteria for serious AE
- Date Investigator became aware of serious AE
- Adverse event is serious due to
- Date of hospitalisation
- Date of discharge
- Probable cause of death
- Date of death
- Autopsy performed
- Causality assessment in relation to study procedure(s)
- Causality assessment in relation to other medication
- Description of AE.

It is important to distinguish between serious and severe AEs. Severity is a measure of intensity whereas seriousness is defined by the criteria in Section 6.3.2. An AE of severe intensity need not necessarily be considered serious. For example, nausea that persists for several hours may be considered severe nausea, but not an SAE. On the other hand, a stroke that results in only a limited degree of disability may be considered a mild stroke but would be an SAE.

#### **Causality collection**

The Investigator will assess causal relationship between the investigational product and each AE, and answer 'yes' or 'no' to the question 'Do you consider that there is a reasonable possibility that the event may have been caused by the investigational product?'

For SAEs causal relationship will also be assessed for other medication and study procedures. Note that for SAEs that could be associated with any study procedure the causal relationship is implied as 'yes'.

A guide to the interpretation of the causality question is found in Appendix B to the CSP.

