## 1.4 Benefit/risk and ethical assessment

There are no direct benefits for the volunteers participating in this study. However, study related health assessments are provided at no cost.

As a consequence of the pharmacological properties of ticagrelor, there is an increased risk for bleeding. However, in this study as only a single dose is administered in each treatment period (within the therapeutic dose range) with adequate washout between the treatment periods, the risk for bleeding has been minimised. Moreover the inclusion and exclusion criteria have considered the contraindication and warning suggested by regulatory approved prescribing information.

Ticagrelor, like other inhibitors of platelet aggregation, increases the risk of bleeding. Reported events in previous Phase II and Phase III studies have included bleeding in areas considered to be clinically important such as the lung, brain, eye, and joints. In previous studies in healthy volunteers, adverse events (AEs) associated with bleeding were infrequent and were generally considered to be mild. In this study, necessary measures will be taken to minimise this risk of bleeding by excluding volunteers at high risk of bleeding such as volunteers with history of haemophilia, von Willebrand's disease, lupus anticoagulant, or other diseases/syndromes that can either alter or increase the propensity for bleeding. Also volunteers with a history of a clinically significant nontraumatic bleed or clinically significant bleeding risk, as judged by the Investigator, will be excluded.

The risk of ticagrelor exposure to volunteers in this study is expected to be equivalent to the safety profile in volunteers observed in previous Phase I studies where similar doses have been administered. The most common AEs, with an incidence of at least 2%, reported to date in the Phase I studies with at least 3 days of ticagrelor dosing include headache, somnolence, dizziness, epistaxis, nausea, abdominal pain, back pain, dyspnoea, ecchymosis, lethargy,

pharyngolaryngeal pain, blurred vision, postural dizziness, pollakiuria (frequent urination), and increased tendency for bruising.

Ticagrelor is well tolerated in single doses up to 900 mg and multiple doses up to 600 mg per day. The highest single dose studied was 1260 mg where adverse gastrointestinal effects limited tolerability and therefore established 900 mg as the maximum tolerated dose.

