Dyspnoea was observed in patients with coronary artery disease (CAD) but rarely in healthy subjects. Ticagrelor does not appear to affect respiratory parameters in elderly subjects, patients with asthma or chronic obstructive pulmonary disease, and stable CAD patients.

When ticagrelor was administered orally to healthy subjects for 5 days under controlled conditions of diet, activity, and fluid intake, serum uric acid levels increased approximately by 10%, with no extreme individual elevations, and returned to baseline within 60 hours of discontinuing ticagrelor.

Ticagrelor (single 900 mg dose) had no cardiac ventricular repolarisation effect during the first 24 hours after administration compared with placebo as assessed by QT interval. In the PLATO study, more patients had ventricular pauses >3 seconds with ticagrelor than with clopidogrel, however, there were no adverse clinical consequences associated with this imbalance (including pacemaker insertions) in this population of patients.

For further relevant pre-clinical and clinical data see the current Investigator's Brochure.

In addition, this study requires application of a nasogastric tube and nose bleeding is not an uncommon effect with nasogastric tube insertion, therefore nasogastric tube will be applied by someone with experience. AstraZeneca will immediately notify the Investigator of important safety data that becomes available during the study.

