#### **Adverse Events**

All AEs will be collected for each volunteer from the time when informed consent is obtained until the follow-up visit. Adverse events that occur before administration of the investigational product will be reported separately.

Adverse events will be summarised by Preferred Term and System Organ Class (SOC) using MedDRA vocabulary (Version 12.0 or higher) by treatment and across all treatments. Furthermore, listings of SAEs and AEs that lead to withdrawal will be made and the number of volunteers who have any AEs, SAEs, AEs that lead to withdrawal, and AEs with severe intensity will be summarised.

All AEs occurring at any time during the study will be listed. All summary tables of AE data will include all AEs starting or worsening after administration of the investigational product. Overall summaries of AEs will be provided at both the volunteer level and the event level, detailing the number of AEs, SAEs, discontinuations due to AEs and other significant AEs by treatment. Adverse events will be summarised by treatment by SOC and preferred term assigned to the event using the MedDRA vocabulary. In volunteer level summaries, a volunteer will only be counted once in each SOC or preferred term. Adverse events will also be summarised by treatment by maximum intensity and by investigator's causality assessment. In addition, separate listings for all SAEs, OAEs, deaths and discontinuations due to AEs will be presented.

Any AEs determined to be of interest or occurring frequently may be summarised separately using the same methodology as described above.

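### Procedure causality is recorded for serious AEs only, so a non-serious nose, throat or nausea event in a nasogastric-tube period cannot be recorded as tube-related, and the causality table for Treatment C may mix tube and drug events

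*Protocol*

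**What the plan says.** Section 6.3.3 (Variables) lists what is recorded for each AE. The only causality item there is "Investigator causality rating against the investigational product (yes or no"). A second list opens with "In addition, the following variables will be collected for SAEs", and causality in relation to study procedures appears only in that list. The Causality collection text in the same section repeats the limit: "For SAEs causal relationship will also be assessed for other medication and study procedures".

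Section 1.4 warns that "nose bleeding is not an uncommon effect with nasogastric tube insertion". The same section lists the common AEs of ticagrelor in Phase I studies, including "headache, somnolence, dizziness, epistaxis, nausea, abdominal pain, back pain, dyspnoea, ecchymosis, lethargy" and, further on, pharyngolaryngeal pain.

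Section 12.2.2 (Adverse Events) puts the causality rating to use: "Adverse events will also be summarised by treatment by maximum intensity and by investigator's causality assessment". The secondary objective (section 2.2) is to examine safety and tolerability for each way of giving the tablet, the tube included.

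**The concern.** One of the three treatments contains an invasive procedure and the other two do not. Its expected minor effects (nosebleed, sore throat, nausea) are also on the drug's own list. For a non-serious event of this kind, the investigator has a single yes/no question about ticagrelor and no field in which to name the tube. A nosebleed that is rarely serious would almost never reach the procedure question.

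What is at stake is how the safety results for C are read. An excess of drug-related nasal or throat events in C could reflect the tube or a change in ticagrelor exposure by that route. These readings mean different things for a patient who would be given the tablet this way. An attribution not captured when the event occurs is hard to rebuild afterwards.

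**Working it through.** The plan states no figure on this point, so there is none to reproduce. The check is a comparison of sections and an illustration of how far the crossover can fill the gap.

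**1. Which causality fields exist (section 6.3.3).**

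| Event | Against ticagrelor | Against study procedures |
|---|---|---|
| Non-serious AE | yes/no | not collected |
| SAE | yes/no | collected |

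The variable list and the causality text agree with each other.

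**2. Where tube events can end up.** Appendix B offers three routes for a nosebleed in C. Fit with the known drug profile is one of the factors that can by itself support a yes. A more likely alternative cause supports a no. An ambiguous case is to be treated as a yes. Similar tube nosebleeds can thus be rated either way. A yes puts the event in the drug-related rows for C. A no leaves it simply unrelated, with the tube not recorded as the cause.

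**3. What the design offers instead.** Section 5.5.2 gives B and C the same crushed 90 mg tablet with 200 mL of water in total; only C uses the tube. Each volunteer is planned to receive both, so C versus B is a paired contrast.

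**4. How strong that contrast is.** The plan sets no AE test; an exact two-sided McNemar test at 0.05 is used here as a yardstick. Sample sizes of 30 evaluable and 36 randomised are from the protocol. The following are assumptions that are not in the documents: event rate in B p_B = 2%, rate in C p_C from 5% to 40%, and B and C events independent within a volunteer.

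Discordant pairs: p10 = p_C(1 − p_B) for an event in C only, and p01 = p_B(1 − p_C) for an event in B only. At p_C = 10%: p10 = 0.10 × 0.98 = 0.098 and p01 = 0.02 × 0.90 = 0.018.

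Fewest pairs that can reach significance: five of five gives 2 × (1/2)^5 = 0.0625, which is not enough; six of six gives 2 × (1/2)^6 = 0.031. At 10% the expected number of volunteers with an event in C is only 30 × 0.10 = 3.

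Power is the sum, over the number of discordant pairs D ~ Binomial(n, p10 + p01), of the probability of a significant result in favour of more events in C:

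| Assumed rate in C | n = 30 | n = 36 |
|---|---|---|
| 5% | 0.2% | 0.4% |
| 10% | 4% | 8% |
| 20% | 42% | 56% |
| 30% | 81% | 90% |
| 40% | 97% | 99% |

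The group contrast can show a common tube effect (about 30% or more) but not an uncommon one (10% or less).

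**5. What the contrast mixes.** C minus B is the tube effect plus the effect of any difference in exposure between the two routes. Exposure by route is what the primary objective sets out to measure, so the contrast has to be read together with the PK results.

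**The case against.** The strongest reply is that the design already separates tube from drug. B is a tube-free control at the same dose, AEs are tabulated by treatment at volunteer and event level, and plasma is sampled 14 times in every period, so altered exposure is measured rather than guessed. Each AE carries verbatim text and start and stop times, the dosing time is defined, and section 12.2.2 allows AEs of interest to be summarised separately. For tolerability of the tube route, tube effects belong to the route, so all-cause AEs by treatment are the relevant summary. The drug list in section 1.4 comes from studies with three or more days of dosing, whereas each period here has a single dose. A procedure rating by an investigator who knows the tube was used is weaker evidence than a randomised contrast.

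Most of this stands. A reader might infer that tube and drug effects cannot be told apart at all; the documents do not support that, for these reasons. A reader might also infer that tube nosebleeds must be rated drug-related; Appendix B permits a no. Nor is there a contradiction within section 6.3.3.

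What the reply does not remove is narrower. None of these sources gives a tabulated attribution for a single event, the contrast is weak when events are few, and the drug-causality table is planned although its one field cannot carry the tube.

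**Conclusion.** The point holds in limited form. It is a data-collection gap, not an error or inconsistency: a non-serious event in a Treatment C period cannot be recorded as procedure-related, so the drug-related rows for C may contain tube events. It affects the reading of the secondary safety objective and leaves the primary PK analysis untouched.

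Its size in events cannot be derived, because the protocol gives no rate for tube-related complaints. Multiplying an assumed rate by 36 insertions would also be too generous, since a nosebleed that starts at insertion begins before the dose goes down the tube. The power figures show only that the C versus B contrast is a partial substitute, and they rest on the assumed 2% rate in B, the assumed range in C, and independence. This is worth fixing as a low-cost improvement, no more.

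**What to change.** In section 6.3.3, move the existing item on causality to study procedures from the SAE list to the list for every AE in all periods, or at least require it for nasal, throat, nausea and bleeding AEs, and amend the Causality collection text to match. In section 12.2.2, add procedure-relatedness to the table by treatment and investigator causality (ticagrelor, procedure, both, neither). Keep the all-cause table by treatment as the main tolerability summary.

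The cost is one existing SAE field carried over to the AE page and one extra split in a table. The downside is a slightly longer AE form and a rating that is subjective in an open-label study, so the new split should support the all-cause comparison and not replace it.
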